	It has been estimated that up to 60% of systemic sclerosis patients will develop interstitial lung disease (ILD). This interstitial disease begins with an inflammatory alveolitis suggesting that anti-inflammatory therapy be of benefit at early stages.
	Systemic sclerosis has the highest case-specific mortality among all systemic autoimmune diseases. Pulmonary hypertension, pulmonary fibrosis, and cardiac complications are among the most frequent causes of death. The single most common cause of mortality is pulmonary fibrosis from ILD.
	There remains a substantial unmet medical need for therapies with improved tolerability and effectiveness for patients with systematic sclerosis.
	The pathogenesis of dcSSc involves a variety of abnormalities, including immunological/inflammatory activation and vascular injury. The important role of T lymphocytes is well established and involves both IL-17-producing helper T cells (Th17) and regulatory T cell (Treg) subsets. Generally, Th17 cells upregulate inflammation and fibrosis while Treg cells provide an immunosuppressive opposing function. An imbalance of these immunomodulatory cell types may contribute to the pathogenesis of dcSSc.
	Several signaling pathways are activated and converge to create the pro-fibrotic state commonly seen in dcSSc. Importantly, extracellular mediators such as transforming growth factor-beta (TGF- β) and Wnt10b cause fibroblast activation and differentiation into myofibroblasts resulting in increased extracellular matrix deposition, collagen cross-linking, matrix remodeling, and tissue stiffness. Thus, fibrotic mechanisms appear to play a central role in the pathogenesis of systemic sclerosis.

Study Rationale

Rho-associated coiled-coil containing protein kinases (ROCK) are members of the serine/threonine kinase family, often studied for their role in cell morphology, motility, and shape through effects on the cytoskeleton. Two ROCK isoforms have been identified: ROCK1 and ROCK2. While both are involved in Rho-mediated changes in the actin/myosin cytoskeletal network, ROCK1 and ROCK2 are not redundant signaling molecules and may serve different functions within cells. Recent research has uncovered additional roles for ROCK signaling, in conditions including autoimmune disease aggravated or caused by a Th17-polarized T cell response and pulmonary fibrosis. Rho GTPase-mediated signaling pathways play a central role in coordinating and balancing T cell mediated immune responses, including T cell receptor-mediated signaling, cytoskeletal reorganization, and the acquisition of the appropriate T cell effector program.

Studies have demonstrated that aberrant activation of ROCK2 leads to induction of interleukin (IL)-17 and IL-21 via interferon regulatory factor 4-dependent mechanism. In addition, ROCK activity was found to be up-regulated in patients with rheumatoid arthritis and systemic lupus erythematosus and inhibition of ROCK2 effectively decreased IL-17 production in vivo and demonstrated efficacy in arthritis and lupus mouse models. Autoimmunity also involves alterations to regulatory T cells that suppress activation of the immune system and play a critical role in maintaining immunological tolerance to self-antigens and inhibiting autoimmune responses. ROCK2 inhibition may increase the suppressive function of regulatory T cells.

ROCK is also downstream of several major pro-fibrotic mediators, including TGF- β , connective tissue growth factor (CTGF), and lysophosphatidic acid. A defining feature of pathologic fibrosis is the differentiation of fibroblasts to myofibroblasts, a process mediated by ROCK. In addition, ROCK mediates stress fiber formation and regulates the transcription of pro-fibrotic genes, including CTGF and alpha-smooth muscle actin (α -SMA). Further, ROCK inhibition has demonstrated anti-fibrotic activity in murine models.

Study Objective(s)

Primary Objectives

The primary objective of this study is to evaluate the efficacy of belumosudil compared to placebo for the Combined Response Index in diffuse cutaneous Systemic Sclerosis (CRISS) at Week 24

Secondary Objectives

[figure not shown]
- To assess the CRISS for each group at Week 52
- To evaluate the efficacy of belumosudil compared to placebo at Week 24 for:
 - Modified Rodnan Skin Score (mRSS)
 - Forced Vital Capacity (FVC)
 - o Physician global assessment
 - o Patient global assessment
 - Scleroderma Health Assessment Questionnaire— Disability Index (SHAQ-DI)

Kadmon Corporation, LLC

Page 6 of 99

27 May 2021

	To evaluate the efficacy of belumosudil at Week 52 compared to baseline for subjects randomized to belumosudil for the parameters in the bullet above
	 To assess changes in lung fibrosis, via high resolution computerized tomography (HRCT), performed at baseline, Weeks 24 and Week 52 only in subjects with ILD at screening
	 To assess pharmacokinetics (PK) of belumosudil by sparse sampling of belumosudil on Weeks 4 and 8 (i.e., Days 29 and 57) immediately prior to belumosudil dosing and 3 hours post- dose
	 To assess the safety of belumosudil compared to placebo in subjects with dcSSc by examining the percentage of subjects with treatment-emergent adverse events (CTCAE v5.0) in subjects with diffuse cutaneous systemic sclerosis
	Exploratory Objectives
	 To evaluate changes in biomarkers of endothelial cell dysfunction, fibrosis, immune system function, and cytokine alterations from subjects receiving belumosudil or placebo
	 To assess histology and gene expression from skin biopsies taken from subjects at baseline, Week 24, and optionally at Week 52
Study Design	Phase 2, double-blind, placebo-controlled, randomized, multicenter trial in subjects with dcSSc with open-label extension.
Methodology	Subjects who have signed an IRB/IEC-approved informed consent form and met all of the inclusion/exclusion criteria will be enrolled. A total of 60 subjects will be randomized into 3 groups (1:1:1) to receive orally administered belumosudil 200 mg once daily (QD; n = 20), belumosudil 200 mg twice daily (BID; n = 20), or matched placebo (n = 20) for 28 weeks. The study will be double-blinded for the first 28 weeks followed by an open-label extension of 24 weeks. After unblinding, the subjects in Group 1 and 2 will continue on the same belumosudil dose whereas the subjects in the placebo group will be re-randomized to one of the belumosudil doses (200 mg QD or 200 mg BID) in 1:1 fashion.
	The primary endpoint will be analyzed using Week 24 data.
	Efficacy will be assessed at baseline and throughout the 52 weeks of dosing period using CRISS, mRSS, PFTs, Physician Global Assessment, and Patient Global Assessment. Safety will be assessed throughout the study.
	Subjects will undergo evaluations as outlined in the Study Assessment

Kadmon Corporation, LLC Page 8 of 99 27 May 2021

- c. Total bilirubin $\leq 1.0 \times$ upper limit of normal (ULN)
- d. Alanine aminotransferase, (ALT), aspartate aminotransferase (AST), and serum creatinine ≤ 1.5 × ULN.
- 7. Female subjects of childbearing potential have a negative pregnancy test at screening. Females of childbearing potential are defined as sexually mature women without prior hysterectomy or who have had any evidence of menses in the past 12 months. However, women who have been amenorrheic for 12 or more months are still considered to be of childbearing potential if the amenorrhea is possibly due to prior chemotherapy, anti-estrogens, or ovarian suppression.
 - a. Women of childbearing potential (i.e., menstruating women) must have a negative urine pregnancy test (positive urine tests are to be confirmed by serum test) documented within the 24-hour period prior to the first dose of study drug.
 - b. Sexually active women of childbearing potential enrolled in the study must agree to use two forms of accepted methods of contraception during the course of the study and for 3 months after their last dose of study drug. Effective birth control includes (i) IUD plus one barrier method; (ii) on stable doses of hormonal contraception for at least 3 months (e.g., oral, injectable, implant, transdermal) plus one barrier method; or (iii) 2 barrier methods. Effective barrier methods are male or female condoms, diaphragms, and spermicides (creams or gels that contain a chemical to kill sperm), or a vasectomized partner.
- 8. For male patients who are sexually active and who are partners of premenopausal women: agreement to use 2 forms of contraception as in criterion number 7 above during the treatment period and for at least 3 months after the last dose of study drug.
- 9. Male subjects must not donate sperm for 3 months after last dose of study drug.
- 10. Able to provide written informed consent prior to the performance of any study-specific procedures.

Exclusion Criteria:

1. Subject has corrected QT interval using Fredericia's formula (QTcF) > 450 ms

	Ongoing use or current use of concomitant medication known to have the potential for QTc prolongation
	3. Female subject who is pregnant or breastfeeding
	4. Participated in another study with an investigational drug within 28 days of study entry (for studies involving biologics, within three half-lives of the biologic)
	5. History or other evidence of severe illness or any other conditions that would make the subject, in the opinion of the Investigator, unsuitable for the study
	6. Chronic heart failure with New York Heart Association Classes II, III, or IV
	7. Acute or chronic liver disease (e.g., cirrhosis)
	8. Positive human immunodeficiency virus (HIV) test
	9. Active hepatitis C virus (HCV), hepatitis B virus (HBV), or positive whole blood tuberculin test
	10. Diagnosed with any malignancy within 3 years of enrollment, with the exception of basal cell or completely resected squamous cell carcinoma of the skin, resected in situ cervical malignancy, resected breast ductal carcinoma in situ, or low-risk prostate cancer after curative resection
	11. Has had previous exposure to belumosudil or known allergy/sensitivity to belumosudil, or any other ROCK2 inhibitor
	12. Scleroderma renal crisis within 4 months prior to enrollment
	13. FVC \leq 50% Predicted.
Test Article(s)	Belumosudil will be provided as 200 mg tablets.
	Matching placebo will be provided during the initial double-blind period as appropriate for subjects in Group 1 and Group 3.
Dosage and Administration	Subjects will be randomized to receive belumosudil 200 mg QD (Group 1), belumosudil 200 mg BID (Group 2), or matched placebo (Group 3) in the blinded 28 weeks as follows:
	Group 1: Belumosudil 200 mg QD (one 200 mg belumosudil tablet AM and one matched placebo PM) will be administered orally daily.
	Group 2: Belumosudil 200 mg BID (one 200 mg belumosudil tablet AM and one 200 mg belumosudil tablet PM) will be administered orally daily.
	Group 3: Matched placebo (one placebo tablet AM and one placebo tablet PM) will be administered orally daily.
	After unblinding, the subjects in Group 1 and 2 will continue on the same belumosudil dose whereas the subjects in the placebo group will be re-randomized to one of the belumosudil doses (200 mg QD or 200 mg BID) in 1:1 fashion.
Reference Therapy	Not applicable.
L	

Duration of Treatment	Study drug dosing will be for 52 weeks: double-blinded for the first 28 weeks followed by an open-label extension of 24 weeks).
Concomitant Treatment	Ongoing immunosuppressive therapy with steroids \le 10 mg per day is permitted.
	All medications a subject receives from the signing of informed consent through the 28-Day Follow-Up visit will be documented.
	 CYP3A4 inhibitors/inducers should be used with caution. Subjects on concomitant medication known to have potential for QTc prolongation will be excluded.
Safety Evaluation	Safety data will be collected from the time the subject signs the informed consent form until 28 days after their last dose of study drug (the adverse event [AE] reporting period). The primary safety outcome will be the percentage of subjects experiencing treatment-emergent AEs (TEAEs) in each group.
	Safety assessments will include AEs, serious adverse events (SAEs), PEs, vital sign measurements (blood pressure, pulse rate, respiratory rate, and temperature), clinical laboratory evaluations (hematology, chemistry and urinalysis), and electrocardiograms (ECGs). Reasons for treatment discontinuation because of toxicity will be documented.
	As this is the first study of belumosudil in subjects with dcSSc, careful monitoring of all toxicities will be carried out.
Efficacy/Activity	Primary Efficacy Endpoint
Evaluation	The primary efficacy endpoint is the effect of belumosudil compared to placebo for CRISS, an exponential algorithm determining the predicted probability of improvement from baseline, incorporating changes in mRSS, FVC % predicted, and physician and patient global assessments. The outcome is a continuous variable between 0.0 and 1.0 (0-100%). A higher score indicates greater probability of improvement. A CRISS score ≥ 20% is considered a clinically meaningful improvement.
	Secondary Efficacy Endpoints
	Secondary efficacy outcomes include the change from baseline in mRSS, FVC, SHAQ-DI, physician global assessment, and patient global assessment for belumosudil-treated and placebo-treated subjects.
	Onset/progression of ILD will be evaluated by the effect of belumosudil compared to placebo in the change in predicted FVC
	In addition, changes in lung fibrosis on HRCT performed at baseline, Week 24 and Week 52 will be assessed only in subjects who have SSc lung disease at screening.
	Exploratory Endpoints
	Exploratory outcome assessments include changes in PD parameters measured in plasma and/or skin biopsy sample (discussed below).
Pharmacokinetics	Sparse PK sampling will be performed on Weeks 4 and 8 (i.e., Days 29 and 57) immediately prior to belumosudil dosing and 3 hours post-dose
Pharmacodynamics	All subjects will have PD blood samples drawn at the following time points prior to dosing: Week 1 (Day 1, baseline), Week 8 (Day 57), Week 24 (Day 169), and Week 52 (Day 365). These samples will be

analyzed to evaluate autoantibody levels at baseline and biomarkers of extracellular matrix turnover which could correlate with both SSc disease activity and disease modification by belumosudil.

All subjects will be required to provide skin biopsies obtained from the dorsal mid-forearm at the Week 1 (Day 1) and Week 24 (Day 169) visits. An optional skin biopsy may be obtained at the Week 52 (Day 365) visit. Biopsy sections will be assessed for histology including fibrosis and inflammation. In addition, gene expression profiling will be performed on skin biopsies.

Statistical Analysis

This proof of concept study will inform future development of belumosudil in dcSSc. The sample size is not driven by hypothesis testing. Two populations will be employed in the analysis of study data:

- The Modified Intent-to-Treat Population (mITT) will consist of all subjects who receive at least one dose of study drug.
- The Evaluable for Efficacy/Activity population will consist of subjects who have received at least 80% of expected study drug and have post-baseline efficacy data.

The primary endpoint will be analyzed on the mITT Population.

Demographics, subject disposition, and baseline characteristics will be summarized in each population and by group.

Efficacy will be evaluated by comparing Week 24 CRISS scores for subjects treated with belumosudil and placebo. Secondary endpoints will include changes in mRSS, FVC, SHAQ-DI, Physician Global Assessment, and Patient Global Assessment from baseline to Week 24 in subjects treated with belumosudil compared to placebo and the change from baseline for subjects with belumosudil at Week 52. No formal comparison will be conducted between the belumosudil QD and belumosudil BID dosing cohorts.

Treatment-emergent AEs will be evaluated using the Common Terminology Criteria for Adverse Events (CTCAE) v 5.0. The total sample size of 20 subjects per belumosudil dose group will provide > 90% probability of one or more belumosudil subjects experiencing an AE that has an underlying rate of $\geq 14\%$ and > 80% probability of one or more subjects in the study experiencing an AE that has an underlying rate of $\geq 10\%$.

The TEAEs will be summarized overall and by group using MedDRA (Version 21.0 or higher) System Organ Class (SOC) and preferred term (PT), classified from verbatim terms. The incidence and percentage of subjects with at least one occurrence of a preferred term will be included, according to the most severe grade using a 5-point scale (mild, moderate, severe, life threatening, or death). The number of events per preferred term will also be summarized. Causality (relationship to study treatment) will be summarized separately.

Adverse events, SAEs, related AEs, related SAEs, \geq Grade 3 AEs, related Grade \geq 3 AEs, and AEs leading to withdrawal, or treatment discontinuation will be summarized overall and by group according to SOC and PTs. Adverse events will also be presented in listings. Duration of AEs will be determined and included in listings, along with action taken and outcome.

Laboratory results will be graded using the CTCAE v5.0. Incidence of laboratory abnormalities will be summarized. The worst on-study grade after the first dose of study drug will be summarized. The incidence of Grade ≥ 3 laboratory abnormalities under treatment and shifts in toxicity grading from baseline to highest-grade post-baseline will be displayed. Vital sign measurements and ECGs will be summarized by group at each scheduled time point using descriptive statistics and included in data listings.

Table of Contents

	L STUDY PROTOCOL	
SPONSO	R APPROVAL SIGNATURE PAGE	3
INVESTI	GATOR SIGNATURE PAGE	4
PROTOC	OL SYNOPSIS	5
1. Introd	luction	. 20
1.1	Background	. 20
1.2	Rho-Associated Protein Kinase	. 20
1.3	Belumosudil Nonclinical Experience	. 21
1.4	Clinical Experience	. 22
1.4.1	Clinical Pharmacokinetics	. 22
1.4.2	Clinical Summary	. 28
1.5	Study Rationale	. 28
1.6	Dose Rationale	. 29
2. Study	Objectives	. 31
2.1	Primary Objective	
2.2	Secondary Objectives	. 31
2.3	Exploratory Objectives	. 31
3. Invest	tigational Plan	. 32
3.1	Study Design	. 32
3.2	Number of Subjects	. 33
3.3	Study Centers	. 33
3.4	Inclusion Criteria	. 33
3.5	Exclusion Criteria	. 35
3.6	Screening	. 35
3.7	Withdrawal Criteria	. 36
3.8	Replacements	. 36
3.9	Treatment Discontinuation	. 36
4. Study	Treatment	. 38
4.1	Investigational Product	. 38
4.2	Dosage and Administration	. 38
4.3	Treatment Assignment	. 38
4.4	Blinding	. 38
4.5	Treatment Compliance	. 39
4.6	Missed Doses	. 39
4.7	Product Accountability	. 40
4.8	Concomitant Medication and Therapies	. 40
4.9	CYP3A4 Inhibitors/Inducers	. 40

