3.1.4.3 Logistic Model Used for Efficacy Analysis with Binary Variables

Treatment comparisons of categorical efficacy variables will be assessed using a logistic regression analysis with treatment in the model. The proportions and 95% CI (Clopper-Pearson (exact) method) will be reported. For each treatment comparison, an estimate of the odds ratio, corresponding Wald 95% CI, and p-value will be presented.

3.1.4.4 Mixed-effects Model of Repeated Measures (MMRM) Used for Efficacy Analysis with Continuous Variables

Treatment comparisons of continuous efficacy variables will be assessed using MMRM analysis at all visits including unscheduled visits prior to or at Week 52.

When the MMRM model is used the model includes treatment, visit and treatment*visit interaction as fixed effects, and subject as random effect. For other efficacy variables, the model includes treatment, week, and baseline values as fixed effects, and subject as random effect. For the CRISS Score if the data is not normally distributed then the rank-transformed values will be used instead. The covariance structure to model the within-patient errors will be unstructured. If the unstructured covariance matrix results in a lack of convergence, the heterogeneous Toeplitz covariance structure, followed by the heterogeneous autoregressive covariance structure, followed by compound symmetry will be used. The Newton-Raphson with ridging optimization technique will be used to aid with convergence. The Kenward-Roger method will be used to estimate the denominator degrees of freedom. Type III tests for the LSM will be used for the statistical comparison; the 95% CI will also be reported. Below is the SAS code for the MMRM analysis.

```
Proc mixed DATA=XX;
Class USUBJID TRT AVISITN;
Model AVAL = TRT AVISITN TRT*AVISITN/ ddfm=KENWARDROGER;
```

```
Repeated AVISITN/Subject=USUBJID type=UN;
lsmeans TRT*AVISITN/diff=control cl alpha=0.05;
Run;
```

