3.1.4.5 Analysis of covariance (ANCOVA) analysis for Efficacy Analysis with Continuous Variables

In addition, treatment comparisons for continuous efficacy variables will also be assessed using an ANCOVA model.

The ANCOVA model includes treatment groups and baseline values. For each treatment comparison performed, the LSM for each treatment group, an estimate of the difference between treatments, corresponding 95% CI and p-value will be presented. Type III sums of squares for the LSM will be used for the statistical comparison. Below is the SAS code for the ANCOVA model.

```
Proc mixed DATA=XX;
Class TRT;
Model AVAL = TRT BASE;
lsmeans TRT / cl alpha=0.05 pdiff;
Run;
```

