3.2 Analysis Populations

Three populations will be employed in the analysis of study data:

- The Modified Intent-to-treat (mITT) Population will consist of all subjects who receive at least 1 dose of study drug.
- The Evaluable for Efficacy/Activity Population will consist of subjects who have received at least 80% of expected study drug and have post-baseline efficacy data.
- The Safety Population is defined as all subjects who receive at least 1 dose of study drug. In this study, the Safety Population is equivalent to the mITT Population.

The primary endpoint will be analyzed on the modified Intent-to-Treat (mITT) Population.

Demographics, subject disposition, baseline characteristics, and efficacy analyses will be summarized in mITT Population and by group.

All safety analyses will be performed on the safety population.

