3.5 Demographics and Baseline Characteristics

3.5.1 Demographics and Other Characteristics

A summary table and a by patient listing will be generated for patient demographics and other characteristics. Variables to be included are: age, sex, race, ethnicity, height, weight, body mass index (BMI), if subjects with ILD (display ILD confirmed diagnosis date in listing), child bearing potential, and other variables as applicable based on indication/study design.

Demographics and other baseline characteristics will be summarized by treatment group in each population.

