3.8.2.2 PFTs

Onset/progression of ILD will be evaluated by the effect of belumosudil compared to placebo in the change in predicted FVC, which is based on institutional standards and will be measured as part of PFTs, including FEV1, FVC, DLco, TLC, and RV.

FVC (%) and change from baseline will be summarized as a continuous endpoint at all scheduled assessment visits. The change from baseline in FVC (%) will be analyzed using the MMRM model. In addition, the change from baseline will be analyzed using the ANCOVA model. Missing data will not be imputed.

FEV1, FVC, DL_{CO}, TLC, RV and their change from baseline will be summarized as a continuous endpoint in subjects with ILD at screening.

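### The FVC% comparison meant to show onset or progression of ILD pools subjects with and without ILD, has no ILD term, and leaves the ILD subset without a treatment estimate

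*Protocol*

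**What the plan says.** The synopsis (Secondary Efficacy Endpoints) sets the purpose: "Onset/progression of ILD will be evaluated by the effect of belumosudil compared to placebo in the change in predicted FVC". Protocol 6.1 and SAP 3.8.2.2 repeat it. ILD is not an entry criterion (Protocol 3.4 and 3.5), so the population is mixed.

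SAP 3.8.2.2 gives the method: "The change from baseline in FVC (%) will be analyzed using the MMRM model", with ANCOVA in addition. The model terms are set centrally. SAP 3.1.4.4 states: "For other efficacy variables, the model includes treatment, week, and baseline values as fixed effects, and subject as random effect". SAP 3.1.4.5 states: "The ANCOVA model includes treatment groups and baseline values". Neither names ILD. SAP 3.2 sets the population: "Demographics, subject disposition, baseline characteristics, and efficacy analyses will be summarized in mITT Population and by group".

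ILD status is used elsewhere. SAP 3.5.1 tabulates it among the baseline variables ("if subjects with ILD (display ILD confirmed diagnosis date in listing"). SAP 3.8.2.6 compares HRCT change between groups in subjects with ILD at screening. For lung function in that subset, SAP 3.8.2.2 covers FEV1, FVC, DLco, TLC and RV, and says that "their change from baseline will be summarized as a continuous endpoint in subjects with ILD at screening". SAP 3.1.4.1 defines descriptive statistics as n, mean, SD, median, minimum and maximum.

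Protocol 3.1, 4.3 and 5.2 describe 1:1:1 allocation and name no stratification factor.

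**The concern.** ILD present at entry can progress only in subjects who have it, and new ILD can arise only in those who do not. A difference in mean FVC% change over both groups shows neither on its own. If belumosudil acts mainly on lungs with ILD, the pooled difference understates that effect. If a pooled difference appears, it cannot be assigned to progression.

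Protocol 9.7.1 says that the main focus is to guide follow-up studies. Whether a later trial should select for ILD is a question these data should inform. As written, the plan gives no FVC% treatment difference with an interval in subjects with ILD. A split made after seeing the data would carry less weight.

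A smaller matter is that ILD status may predict FVC% change. Leaving it out of the model, with no stratification stated, lets chance differences in ILD share between small arms add noise to the estimate.

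**Working it through.** **Inputs**
- Arm size 20, allocation 1:1:1 (Protocol 9.7.2, SAP 3.1.3). Two-sided 0.05 (SAP 3.1.4.4 and 3.1.4.5).
- ILD share p at screening: not given for this trial. The synopsis offers only a general figure: "It has been estimated that up to 60% of systemic sclerosis patients will develop interstitial lung disease (ILD". Assumed 0.3 to 0.6.
- FVC% effect in ILD: not given. For illustration 4 points, from 5% minus 1% in the sponsor's open-label IPF study (Protocol 1.4.1.2).
- SD of FVC% change: not given; assumed 5 to 8 points. Gap in mean FVC% change between ILD and non-ILD subjects: not given; assumed 2 to 6 points.

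The plan states no FVC power or effect size to reproduce. Its only probability tied to 20 subjects concerns adverse events. That one checks (1 − 0.86^20 = 95.1%; 1 − 0.90^20 = 87.8%) but has no bearing here.

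**Dilution.** Let the effect be δ in ILD subjects and rδ in the others. The pooled effect is δ[p + (1 − p)r]. With r = 0 it is pδ, that is 0.3δ to 0.6δ. With r = 1 it is δ, so there is no dilution.

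**Which contrast is more sensitive.** With equal SD, the z-value for the ILD subset divided by the pooled z-value is √p / [p + (1 − p)r].
- r = 0: 1/√p = 1.29 at p = 0.6 and 1.83 at p = 0.3.
- r = 1: √p = 0.77 and 0.55.
- The two are equal at r = √p/(1 + √p) = 0.44 and 0.35. Above that the pooled contrast is more sensitive.

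**Illustrative power** (4 points in ILD, SD 6, normal approximation):

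| ILD share | Pooled, effect only in ILD | Pooled, same effect in all | ILD subset |
|---|---|---|---|
| 0.6 (12 per arm) | 24% (pooled effect 2.4) | 56% | 37% |
| 0.3 (6 per arm) | 9% (pooled effect 1.2) | 56% | 21% |

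Over SD 5 to 8 and p 0.3 to 0.6, with the effect only in ILD, the pooled contrast has 7–33% power and the ILD subset 14–50%. Power is low either way, so the gain lies in an estimate with an interval.

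**Chance imbalance.** ILD counts in two arms are independent Binomial(20, p). The SD of the difference in share is √[2p(1 − p)/20] = 0.155 at p = 0.6. The exact probability of a difference of at least 4 of 20 is 22.6% at p = 0.3, 25.8% at 0.4, 26.8% at 0.5 and 25.8% at 0.6. For at least one of the two dose-placebo comparisons it is 37% at p = 0.3 and 42% at 0.6 (simulation, 400,000 draws).

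**What an imbalance does.** A 20-point difference shifts the contrast by 0.2 times the gap between ILD and non-ILD subjects: 0.4, 0.8 or 1.2 FVC% points for gaps of 2, 4 or 6, before baseline adjustment. As a share of the contrast's variance, at p = 0.6, gap 4 and SD 6: (4 × 0.155)² = 0.384, against a sampling variance of 2 × 36/20 = 3.6, so 0.384/3.984 = 9.6%. Over the assumed ranges the share is about 1% to 27%, and less where baseline FVC% already carries it.

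**Precision of an ILD-subset estimate.** Standard error relative to 20 per arm: √(20/12) = 1.29 and √(20/6) = 1.83, so intervals about 29% and 83% wider.

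**The case against.** The strongest reply is that the pooled FVC analysis fits its listed objective. Protocol 2.2 and SAP 2.1.2 ask for FVC at Week 24, belumosudil against placebo, with no restriction to ILD. The restricted objective is HRCT. The stated aim also includes onset, so subjects without ILD belong in the analysis, and FVC is their main scheduled lung measure. This stands, and it is why the pooled contrast should be kept.

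A reader might infer that the plan rests on one FVC comparison and has no ILD-specific lung comparison. The documents do not support that. There are two doses against placebo, each by two models, and HRCT change is compared between groups within ILD. CRISS Step 1 (SAP 3.8.1) also scores new or worsening lung fibrosis as 0.0. None of these, however, gives an FVC% treatment difference in subjects with ILD.

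A reader might also infer that the ILD subset is bound to be more sensitive. That needs little or no effect outside ILD, which the documents do not show.

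Baseline FVC% does adjust for part of any imbalance, and ILD is tabulated by group. But subjects with the same FVC% may or may not have ILD. In addition, the printed MMRM code in SAP 3.1.4.4 omits the baseline term that its text includes.

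Finally, the group without ILD is not confirmed by imaging. Protocol 5.1 lists no screening HRCT, and Appendix A limits HRCT to subjects with confirmed ILD. That limits what a separate result there can mean.

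**Conclusion.** The point holds as a gap between stated purpose and planned output. FVC% is to answer a question about ILD onset and progression, but no modelled FVC% comparison uses ILD status and the ILD-subset FVC results carry no treatment difference. If the effect is confined to ILD, the pooled estimate is 30–60% of it; if the effect is uniform, nothing is lost by pooling. Both statements depend on an assumed ILD share of 0.3–0.6, and the comparison of z-values also on equal SD.

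It would go too far to say that imbalance biases the FVC% result. Randomization makes it random error already reflected in the interval, and probably a modest part of the variance. Nor would a subset analysis have adequate power. The trial is declared exploratory, and the benefit is a prespecified estimate with its uncertainty. The change is worth making because it affects what can be concluded about progression. The primary CRISS analysis is not affected.

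**What to change.** In SAP 3.8.2.2:
1. Add ILD at screening (yes/no) as a main-effect covariate in the FVC% MMRM and ANCOVA. Keep the pooled adjusted difference as the answer to the general FVC objective. Reconcile the MMRM text and code on the baseline term.
2. For the ILD subset already summarised, report the Week 24 belumosudil-placebo difference in FVC% change with its 95% confidence interval, from an ANCOVA on treatment and baseline FVC%. Give the same estimate in subjects without known ILD. Label both exploratory.
3. State in SAP 3.8.2.2, and align the synopsis and Protocol 6.1, that the pooled contrast alone is not reported as ILD progression.

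A treatment-by-ILD-by-visit MMRM is not advised. With seven scheduled post-baseline FVC visits to Week 52 it would have 3 × 2 × 7 = 42 cell means and 7 × 8/2 = 28 unstructured covariance parameters for 60 subjects.

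The cost is one degree of freedom in each model, one extra table and a few lines of text, with no new data. The subset intervals will be wide, and the result in subjects without known ILD needs a caution because no scheduled trial HRCT confirms their status.
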